 - e. Percent change in IgG antibody levels from vaccination day #1 to #2, and from vaccination day #2 to #3 will be compared between vaccine formulation and dose groups to assess the sustainability of the response from trough to trough. Values will be reported with 95% confidence intervals.
 - f. Percent change in IgG antibody levels from the peak following the third vaccination, to 3, 6 and 9 months after the third vaccination. Values will be reported with 95% confidence intervals.
 - g. Geometric mean antibody responses for each antigen will be compared using a regression model at each time point with main effects for the doses of Na-APR-1 (M74) (10, 30 or 100µg), GLA-AF (0 or 5µg), and Na-GST-1 (0, 100µg)
 - h. For antigen-specific log IgG levels, three-way ANOVAs will be conducted, with Na-APR-1 (M74) dose, GLA-AF dose, and Na-GST-1 co-administration status as factors.
 - i. A longitudinal model will be built to describe the IgG levels over time. Using a longitudinal panel model, differences in antibody isotype levels by dose and formulation of Na-APR-1 (M74) and Na-GST-1 co-administration status will be explored. This will be accomplished using Proc Mixed in SAS 9.3 so the analysis will take account of the correlation between measurements on the same participant.

Tertiary Objective 2: To assess the impact of co-administration of Na-GST-1 on the distribution of IgG subclass responses to Na-APR-1 (M74) and vice versa.

Tertiary Outcome Measure 3: The IgG subclass distribution (IgG1, IgG3, and IgG4) by plate based ImmunoCAP on approximately Day 126.

Tertiary Outcome Measure 4: The IgG subclass distribution by plate based ImmunoCAP each day of vaccination, approximately 28 days later, and approximately 3 and 6 months after the final vaccination.

Analysis Plan:

- a. The proportion of subjects with detectable anti-Na-GST-1 and anti-Na-APR-1 (M74) IgG subclass responses will be summarized at each time point as a descriptive measure.
- b. IgG subclass antibody levels will be displayed graphically by study group using notched box plots at each time point.
- c. Geometric mean antibody responses will be compared between vaccine formulation and dose groups. Comparisons between groups will be made by a one-way analysis

-
- of variance (ANOVA) with pair-wise comparisons between groups made by contrasts.

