- d. For antigen-specific IgG subclass (IgG1-IgG4) levels, a three-way ANOVA will be conducted, with Na-APR-1 (M74) and GLA-AF doses, and Na-GST-1 co-administration status, as factors.
 - e. A longitudinal model will be built to describe each of the antibody isotype levels over time for each of IgG1-IgG4. Using a longitudinal panel model, differences in antibody isotype levels by dose and formulation of Na-APR-1 (M74) and Na-GST-1 co-administration status will be explored. This will be accomplished using Proc Mixed in SAS 9.3 so the analysis will take account of the correlation between measurements on the same participant.

Tertiary Objective 3: To assess the impact of co-administration of Na-GST-1 and Na-APR-1 (M74) on the functional capacity of vaccine-induced antibodies to neutralize the *in vitro* activity of the native enzymes (Na-GST-1 and wild type Na-APR-1).

Tertiary Outcome Measure 5: The functional capacity of vaccine-induced antibodies to neutralize the *in vitro* activity of the native enzymes.

Analysis Plan:

- a. Percent inhibition of native enzyme activity will be displayed graphically for the various study groups at each time point.
- b. Three-way ANOVAs with Na-APR-1 (M74), Na-GST-1, and GLA-AF as factors and percent inhibition as the outcome will be estimated.
- c. A longitudinal model will be built to describe percent inhibition of native enzyme activity over time. Using a longitudinal panel model, differences in percent inhibition by dose and formulation of Na-APR-1 (M74) and co-administration with Na-GST-1 will be explored. This will be accomplished using Proc Mixed in SAS 9.3, so the analysis will take account of the correlation between measurements on the same participant.

Tertiary Objective 4: To assess the impact of co-administration of Na-GST-1 and Na-APR-1 (M74) on the affinity of the antibody interactions with both recombinant antigens.

Tertiary Outcome Measure 6: The affinity of the antibody interactions with both recombinant antigens at approximately 7, 14, and 28 days after each vaccination, and 3, 6, and 9 months after the third dose.

Analysis Plan:

- a. Antibody affinity will be displayed graphically for the various study groups at each time point.
- b. Three-way ANOVAs with Na-APR-1 (M74), Na-GST-1, and GLA-AF as factors and overall affinity as the outcome will be estimated.

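### Tertiary Objective 2 asks about the IgG subclass distribution, but no planned test separates a uniform change in antibody from a change in subclass balance

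*Protocol*

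**What the plan says.** Section 11.4 states Tertiary Objective 2 as "To assess the impact of co-administration of Na-GST-1 on the distribution of IgG subclass responses to Na-APR-1 (M74) and vice versa". Two outcome measures serve it. Outcome Measure 3 is "The IgG subclass distribution (IgG1, IgG3, and IgG4) by plate based ImmunoCAP on approximately Day 126". Outcome Measure 4 begins "The IgG subclass distribution by plate based ImmunoCAP each day of vaccination, approximately 28 days later" and continues to 3 and 6 months after the last dose; it names no particular subclasses.

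Five analyses are assigned to these outcomes:

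- **a.** The proportion with detectable "IgG subclass responses will be summarized at each time point as a descriptive measure".
- **b.** Notched box plots of the level of each subclass.
- **c.** "Geometric mean antibody responses will be compared between vaccine formulation and dose groups", by one-way ANOVA with contrasts.
- **d.** "For antigen-specific IgG subclass (IgG1-IgG4) levels, a three-way ANOVA will be conducted". The three factors are the dose of the APR-1 antigen, the dose of GLA-AF, and whether Na-GST-1 was given.
- **e.** A longitudinal model of the level of each of IgG1 to IgG4, fitted with Proc Mixed.

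Tests are two-sided at 5%. The section calls itself a brief description and promises a detailed analytical plan.

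**The concern.** A distribution concerns how the response is divided among subclasses. Every listed analysis instead looks at one subclass at a time. Subclass is not a factor in item d, item e is run separately for each subclass, and no analysis forms a share, a ratio or an interaction.

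Two problems follow. If co-administration lowers all IgG in proportion, the subclass tests respond although the balance has not moved. If it shifts the response from one subclass to another, the evidence is split over separate tests that ignore the correlation within a person.

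The amount of antibody is already the secondary objective. What Tertiary Objective 2 adds is the kind of antibody, and Section 2.1.8 gives that meaning by arguing from the isotype pattern to the suitability of the vaccine. The protocol itself fixes both the question and the response variable, so this is a mismatch within its text and not merely a detail left to a later plan.

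There is also a smaller inconsistency. Outcome Measure 3 lists three subclasses (IgG1, IgG3, IgG4), while item d covers four.

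**Working it through.** **Plan's own figures.** The protocol gives none for this objective. Its only sample-size figures are the event probabilities in Section 11.2, which follow 1 − (1 − p)^n (for example 1 − 0.95^30 = 78.54%). All 15 cells reproduce, and they have no bearing here.

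**Inputs**

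- From the protocol: six Groups, each with 5 subjects given Na-GST-1 and 5 given saline, so 6 × 5 = 30 versus 30; two-sided 5%.
- From Table 1 (Section 2.1.8, natural infection, not vaccinees): mean ± SD of 0.195 ± 0.104 (IgG1), 0.123 ± 0.066 (IgG3) and 0.203 ± 0.136 (IgG4) µg/ml. If log-normal, log SD = √ln(1 + (SD/mean)²), about 0.50 to 0.61.
- Assumed, because the protocol gives no values: correlation between log subclass levels 0.3-0.7, widened to 0.3-0.9 in the second check; log SD after vaccination 0.5-1.2.

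**Step 1. A uniform change leaves the distribution alone.** The Table 1 means sum to 0.521, giving shares of 37.4%, 23.6% and 39.0%. Doubling all three gives 0.390, 0.246 and 0.406 out of 1.042, which are the same shares.

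**Step 2. Uniform fall of 0.8 SD** (20,000 simulated trials per setting, two-sample t tests, all values quantifiable):

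| Correlation | At least one of three level tests significant | All three significant | Some but not all | Log-ratio IgG1/IgG4 significant |
|---|---|---|---|---|
| 0.3 | 99% | 68% | 31% | 5% |
| 0.5 | 97% | 71% | 27% | 5% |
| 0.7 | 95% | 74% | 21% | 5% |

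**Step 3. True switch: IgG1 down 0.4 SD, IgG4 up 0.4 SD.** Power of a single level test at d = 0.4 with 30 per arm is 33%. At least one of three is significant in about 61-64% of trials. The standardised effect on the log-ratio is 0.8/√(2(1 − ρ)):

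- ρ = 0.3: 0.8/√1.4 = 0.676, power 73%
- ρ = 0.5: 0.8/√1.0 = 0.800, power 86%
- ρ = 0.7: 0.8/√0.6 = 1.033, power 98%

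**Step 4. Check in the 3 × 2 × 2 layout** (5 per cell, main-effects model, 2,000 runs per setting, log SD 0.5-1.2, correlation 0.3-0.9). With a uniform two-fold change, one given level test is significant in 58-100% of trials and at least one of three in 70-100%; the joint log-ratio test is significant in 4.7-5.9%. With a uniform 1.5-fold change the figures are 34-99% for at least one and 3.8-6.0% for the ratio test. With IgG1 × 1.3 and IgG4 ÷ 1.3 at log SD 0.8, at least one level test is significant in 49%, against 70% (correlation 0.6) to nearly 100% (0.9) for the ratio test.

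**Step 5. Effect of an assay floor on the ratio.** This repeats Step 2 with values below the limit replaced by the limit, assuming 95% IgG1 detection in the arm without the fall. If IgG4 is detectable in 53% of that arm, the log-ratio test is falsely significant in about 41-57% of trials; at 15%, in about 78-82%. Table 1 reports 53% for IgG4 and 15% for IgG3 in infected residents. Detection after vaccination is not given, so these are illustrative values.

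**The case against.** Several points on the other side have force.

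- **Reporting is not specified.** A reader might infer that a uniform fall would be reported as a changed distribution. The protocol nowhere says how subclass results will be worded, so the documents support only that a mixed pattern could be misread.
- **The pattern is not invisible.** It is tempting to say the plan cannot separate less antibody from different antibody. That is too strong. Item c works with geometric means, and the difference between two subclasses' log geometric-mean effects is the mean log-ratio effect, at least for unadjusted complete data. Total IgG on Day 126 is compared under the secondary objective, so parallel shifts could be seen. What is missing is a standard error and a test for the difference.
- **Distribution is not defined.** Table 1 presents subclasses as percent positive and mean level, so the authors may have meant a profile of levels. In that case rewording would be enough.
- **Ratios have their own weakness.** Step 5 shows that a log-ratio with limit substitution can make much the same error. This rules out replacing the level analyses with simple ratios.
- **The 30 versus 30 figures cover half the objective.** The anti-Na-GST-1 comparison relies on stored SVI-10-01 specimens (Section 11.4), which are not randomised against this trial's subjects and have a different sample size.
- **IgG2 is a narrow point.** Outcome Measure 4 lists no subclasses, so item e does not contradict it. Only item d against Outcome Measure 3 does.
- **Consequences are limited.** Section 11.1 disclaims formal hypothesis testing and lists no subclass hypothesis. The decision on paediatric testing (Section 15.4) uses safety and ELISA IgG.

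All of this stands, and it limits the reach and severity of the point. It does not remove the gap between the stated question and the tests assigned to it.

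**Conclusion.** The point holds as a low-severity mismatch. For anti-Na-APR-1, level tests in single subclasses respond strongly to a uniform change: 95-99% for at least one of three at 0.8 SD, against 5% for a within-subject contrast. They are also less sensitive to a true switch: about 61-64% against 73-98%. These sizes rest on assumed correlations and effects and on fully quantifiable values. Near the assay floor the advantage of a simple ratio largely disappears. The documents do not support the stronger claims that a uniform change would be reported as a shift, or that the planned output hides the difference altogether. The inconsistency between item d and Outcome Measure 3 needs no assumption.

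**What to change.** Keep items a to e and add one analysis designated as the test for Tertiary Objective 2.

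- **Anti-Na-APR-1:** a mixed model on log subclass levels with subclass as a within-subject factor, adjusted for Group (with Group effects allowed to differ by subclass), testing the co-administration-by-subclass interaction. This is equivalent to comparing within-subject log-ratios.
- **Values below the assay limit:** treat them as left-censored and do not substitute the limit. Leave any subclass that is mostly undetectable out of the contrast and report it as percent detectable.
- **Anti-Na-GST-1:** make the same contrast against the stored SVI-10-01 specimens and label it non-randomised.
- **Subclass set:** reconcile item d with Outcome Measure 3 by dropping IgG2 from the item or adding it to the outcome.

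If only levels were intended, reword the objective and both outcome measures as subclass levels; no new test is then needed.

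The cost is protocol or analysis-plan wording, a censoring rule and a little more analysis work. No further subjects, samples or assays are required, unless IgG2 is added to the outcome and is not already being measured.

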2.1.8 Studies of Human Immune Responses to *Na*-APR-1 in Endemic Areas

To assess serologic recognition of *Na*-APR-1_{mut} by humans resident in areas of high transmission for *N. americanus*, sera from 648 hookworm-infected individuals from Minas Gerais state, Brazil, were screened for anti-APR-1_{mut} antibody responses. Sixty-two percent showed detectable IgG responses (42% had IgG1, 0.6% IgG2, 15% IgG3, 53% IgG4) and only 0.6% had IgE antibodies to *Na*-APR-1_{mut} (Table 1). There was no association between the presence of antibody and current infection status (positive or negative), intensity of infection (EPG), or age.

Table 1: Anti-*Na*-APR-1_{mut} IgG, IgG subclasses (IgG1-4), IgE, and IgA Antibodies in Brazilian Individuals Living in a Hookworm-Endemic Area.

ELISA method	IgG1	IgG2	IgG3	IgG4	Total IgG	IgE	IgA
Dichotomous, positive [% (n)] ^a	42 (270)	0.6 (4)	15 (97)	53 (343)	62 (401)	0.6 (4)	3 (22)
Quantitative (µg/ml) ^b	0.195 ± 0.104	– ^c	0.123 ± 0.066	0.203 ± 0.136	0.592 ± 0.518	–	–

^a Positivity as indicated by a reactivity threshold, which was determined from a frequency distribution from the upper 95% CI of the frequency distribution from log₁₀ transformed OD values from a panel of sera from Brazilian volunteers not resident in an *N. americanus* transmission area (n=56) and a panel of control sera from U.S. volunteers (24).

^b Values are means ± SD. Amounts were not calculated for samples in which <25 individuals were positive for the antibody.

^c Heterologous interpolation of antibody levels to *Na*-APR-1_{mut} refers to a calibration scheme in which the calibration curve uses reagents that have a different specificity from those used to measure the analyte of interest; in this case, *Na*-APR-1_{mut}-specific antibody ELISA was simultaneously performed alongside a total Ig assay, with the mass values calibrating by interpolating the sample values by the standard curve of the total Ig assay.

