3.2.3 Tertiary Outcome Measures

Immunogenicity

The following parameters will be evaluated for each dose and formulation of *Na*-APR-1 (M74) alone or co-administered with *Na*-GST-1:

1. The IgG antibody response, by an indirect enzyme-linked immunosorbent assay (ELISA) at approximately 7, 14, and 28 days after each vaccination, and approximately 3, 6, and 9 months after the third dose.

2. The IgG antibody response, by ImmunoCAP at approximately 7, 14, and 28 days after each vaccination, and approximately 3, 6, and 9 months after the third dose.
3. The IgG subclass distribution (IgG1, IgG3, and IgG4) by plate based ImmunoCAP on approximately Day 126.
4. The IgG subclass distribution by plate based ImmunoCAP each day of vaccination, approximately 28 days later, and approximately 3 and 6 months after the final vaccination.
5. The functional capacity of vaccine-induced antibodies to neutralize the *in vitro* activity of the native enzymes.
6. The affinity of the antibody interactions with both recombinant antigens at approximately 7, 14, and 28 days after each vaccination, and 3, 6, and 9 months after the third dose.
7. The production of memory B cells specific for each antigen on days of vaccination, approximately 28 days following each vaccination, and 6 and 9 months after the third dose.

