5.3.2 Masking Procedures

Due to the staggered, dose-escalation design of the trial, it will not be possible to blind to *Na*-APR-1 (M74)/Alhydrogel[®] dose assignment or GLA-AF co-administration assignment. That is, those subjects enrolled into Group 1 will receive either 10µg *Na*-APR-1 (M74)/Alhydrogel[®] administered to one arm and sterile saline administered to the alternate arm, or 10µg *Na*-APR-1 (M74)/Alhydrogel[®] in one arm and 100µg *Na*-GST-1/Alhydrogel[®] administered to the alternate arm. Subjects enrolled into Group 2 will receive either 10µg *Na*-APR-1 (M74) /Alhydrogel[®] plus 5µg GLA-AF administered to one arm and sterile saline administered to the alternate arm, or 10µg *Na*-APR-1 (M74) /Alhydrogel[®] plus 5µg GLA-AF in one arm and 100µg *Na*-GST-1/Alhydrogel[®] administered to the alternate arm, and so on.

Investigators and subjects will be blinded to the within-Group random allocation to receive co-administered sterile saline or *Na*-GST-1/Alhydrogel[®] until all subjects have completed their Day 140 visit, the safety and secondary immunogenicity outcomes (i.e., anti-*Na*-GST-1 and anti-*Na*-APR-1 (M74) IgG antibody results by ELISA) have been monitored and entered into the database, and the database has been “soft-locked” for interim analysis. Procedures to maintain blinding include administering two injections to all subjects at each vaccination point. For this, sterile saline will be co-administered to those subjects randomized to receive *Na*-APR-1 (M74) without co-administration of *Na*-GST-1.

The study vaccine manager will also prepare all investigational product doses (vaccine or sterile saline placebo) in a separate room, and will hand filled syringes to the vaccinator(s). Since the 10 and 30µg doses of the *Na*-APR-1 (M74) formulations are of different volumes (0.1 and 0.3ml, respectively for administration without GLA-AF) than that of *Na*-GST-1, the contents of all syringes will be disguised using opaque tape. As a further precaution, the vaccinator(s) will not be involved in assessments of reactogenicity or adverse events.

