8.2.2.1 Anti-*Na*-APR-1 (M74) and Anti-*Na*-GST-1 Antibody Assays

Antibodies to *Na*-APR-1 (M74) and *Na*-GST-1 will be measured in serum or plasma of study subjects using two different methods for comparison: a) a conventional qualified indirect enzyme-linked immunosorbent assay (ELISA) technique using a Standard Reference Serum; and, b) a custom made ImmunoCAP (Phadia, Inc.) for each antigen (*Na*-GST-1 and *Na*-APR-1 (M74)). Antigen-specific IgG and IgG subclass antibody levels will be measured by ELISA and ImmunoCAP at baseline and at several time-points post-vaccination as outlined in Section 3 and in Appendix B. For the qualified conventional indirect ELISA, 96 microwell plates are coated with purified recombinant *Na*-APR-1 (M74) or *Na*-GST-1, blocked, and incubated with serial dilutions of a positive “standard reference serum” pool to generate a reference curve from which antibody levels of test sera can be interpolated. After washing, a horseradish peroxidase conjugated goat anti-human antibody will be added and incubated with plates, washed again, incubated with a chromogenic substrate, and antibody levels measured on an ELISA plate reader.

Qualified ELISAs (one each for *Na*-GST-1 and *Na*-APR-1 (M74)) will also be used to detect IgE antibodies to each antigen, as screening tests to determine eligibility for study participation. If

during screening for volunteer participation in the study, serum samples with anti-*Na*-GST-1 IgE results by ELISA are greater than the reactivity limit, they will then be tested by the ImmunoCAP method for confirmation. The ImmunoCAP method is considered to be the gold standard for measuring levels of antigen-specific IgE in serum. The ImmunoCAP tests will be performed at the DACI Reference Laboratory of Johns Hopkins University.

Surface Plasmon Resonance (SPR) will be used to measure the affinity of antibody interactions with both recombinant antigens. SPR determines the immunoreactivity and affinity of antibody responses in numerous contexts as it measures rates of antibody-antigen association and dissociation based on the Law of Mass Action to assess antibody affinity.

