As illustrated in the table above, the study will have high probability ($\geq 80\%$) of detecting events that are commonly occurring in the population. For example, with a sample of 20 participants (which is equivalent to the size of each dose group of *Na*-APR-1 (M74) in this study), there is an 87.84% probability of observing 1 or more events when the events occur at a rate of 10.0% in the population. As the sample size increases, the study is able to detect events that occur at lower rates. For example, using a sample size of 30 participants (which is equivalent to the number of participants assigned to vaccine co-administration in this study vs. *Na*-APR-1 (M74) alone), there is a 78.54% probability of observing 1 or more events that occur at a rate of 5% in the population. Using a sample of size 60 (equivalent to the entire study population) there is an 83.92% probability of observing 1 or more events that occur at a rate of 3% in the population. Detection of rare events—those that occur at a rate of 1% or less in the population—is not likely in this study.

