2. The IgG level by ImmunoCAP on approximately Day 126.

Analysis Plan:

- a. The proportion of participants with detectable anti-Na-GST-1 and anti-Na-APR-1 (M74) responses will be summarized as a descriptive measure.
- b. IgG levels will be displayed graphically by study group using notched box plots.
- c. Geometric mean antibody responses will be compared between vaccine formulation and dose groups. Comparisons between groups will be made by a one-way analysis of variance (ANOVA) with pair-wise comparisons between groups made by contrasts.
- d. Geometric mean antibody responses for each antigen will be compared using a regression model with main effects for the doses of Na-APR-1 (10, 30 or 100µg), GLA-AF (0 or 5 µg), and Na-GST-1 (0, 100µg).
- e. For antigen-specific log IgG levels, a three-way ANOVA will be conducted, with Na-GST-1, Na-APR (M74) and GLA-AF doses as factors.
- f. Pair-wise comparisons across all combinations of Na-APR-1 (M74) doses, GLA-AF doses (i.e., 0 or 5 µg), and Na-GST-1 co-administration status will be assessed using Tukey's HSD.

Tertiary Objective 1: To assess the impact of co-administration of Na-GST-1 on the duration of the antibody responses to Na-APR-1 (M74), and vice versa.

Tertiary Outcome Measure 1: The IgG antibody response, by an indirect enzyme-linked immunosorbent assay (ELISA) at approximately 7, 14, and 28 days after each vaccination, and approximately 3, 6, and 9 months after the third dose.

Tertiary Outcome Measure 2: The IgG antibody response, by ImmunoCAP at approximately 7, 14, and 28 days after each vaccination, and approximately 3, 6, and 9 months after the third dose.

Analysis Plan:

- a. The proportion of participants with detectable anti-Na-GST-1 and anti-Na-APR-1 (M74) responses will be summarized as a descriptive measure.
- b. Antigen-specific IgG levels will be displayed graphically by study group using notched box plots at each time point.

-
- c. Geometric mean antibody responses will be compared between vaccine formulation and dose groups at each time point. Comparisons between groups will be made by a one-way analysis of variance (ANOVA) with pair-wise comparisons between groups made by contrasts.
 - d. Percent change in IgG antibody levels from days of vaccination to days 7,14 and 28 will be compared between vaccine formulation and dose groups. Values will be reported with 95% confidence intervals.

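### For anti-Na-GST-1 affinity, the Na-GST-1 factor in the planned three-way ANOVA cannot show the effect of co-administration

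*Protocol*

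**What the plan says.** Protocol section 3.2.3 makes affinity a tertiary outcome for both antigens, from the first week after dose 1: "The affinity of the antibody interactions with both recombinant antigens at approximately 7, 14, and 28 days after each vaccination", with later visits to 9 months after dose 3. Section 8.2.2.1 measures it by surface plasmon resonance; "it measures rates of antibody-antigen association and dissociation based on the Law of Mass Action to assess antibody affinity".

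Under Tertiary Objective 4 in section 11.4, plan b reads: "Three-way ANOVAs with Na-APR-1 (M74), Na-GST-1, and GLA-AF as factors and overall affinity as the outcome will be estimated". Plan c adds a mixed model over time that explores differences by Na-APR-1 dose and formulation and by co-administration with Na-GST-1. Neither plan separates the two antigens.

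On the design, section 5.3.2 says that "sterile saline will be co-administered to those subjects randomized to receive" Na-APR-1 without Na-GST-1. Section 11.2 describes 30 participants, "which is equivalent to the number of participants assigned to vaccine co-administration in this study vs" Na-APR-1 alone. For the IgG regression under the secondary objective, section 11.4 lists the factor levels as "main effects for the doses of Na-APR-1 (10, 30 or 100µg), GLA-AF (0 or 5 µg), and Na-GST-1 (0, 100µg"). No zero level of Na-APR-1 appears.

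A note near the start of section 11.4 says that safety data, stored serum and cells from SVI-10-01, run at the same site, will represent Na-GST-1 given without Na-APR-1, and that those specimens will be assayed together with the new ones. Plans b and c for affinity do not mention them.

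**The concern.** Affinity is a property of antibody that binds. A sample with no anti-Na-GST-1 antibody has no anti-Na-GST-1 affinity: the value is undefined, not low. An IgG titre below detection can be given a floor value, but an affinity cannot. Carrying the IgG factor structure over to affinity therefore leaves the saline level of the Na-GST-1 factor either empty or filled with natural antibody only.

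The fourth hypothesis in section 11.1 is that giving the vaccines together does not reduce avidity to either antigen relative to each given alone. For Na-GST-1 that means Na-GST-1 with Na-APR-1 against Na-GST-1 without it. The printed factor makes a different comparison: Na-GST-1 recipients against subjects never given that antigen. An analyst following plan b would get no estimate, or an estimate that a reader could mistake for evidence on interference.

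**Working it through.** **Stated figure.** The plan gives no power, effect size or SD for affinity, so there is none to reproduce. Its only calculated figures are the event-detection probabilities in section 11.2. They follow from 1 − (1 − p)^n (for example 1 − 0.95^30 = 78.54%), and all 15 entries agree. They do not bear on this point.

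**Step 1: the design.** Three Na-APR-1 doses × two GLA-AF levels × two Na-GST-1 levels = 12 cells; 12 × 5 = 60 subjects. Saline cells: 3 × 2 = 6, so 6 × 5 = 30 subjects.

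**Step 2: which contrast answers the question.**

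| | Na-GST-1 given | Na-GST-1 not given |
|---|---|---|
| Na-APR-1 given | 30 | 30 |
| Na-APR-1 not given | 0 | 0 |

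- Anti-Na-APR-1 affinity needs both vaccines against Na-APR-1 alone: 30 against 30, randomised. The Na-GST-1 factor is the right one.
- Anti-Na-GST-1 affinity needs both vaccines against Na-GST-1 alone: 30 against 0 within the trial. No factor in the trial's own data estimates it.

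**Step 3: estimability if no saline recipient has a value.** The main-effects model has 1 (intercept) + 2 (Na-APR-1 dose) + 1 (GLA-AF) + 1 (Na-GST-1) = 5 columns. With all 60 subjects its rank is 5. With only the 30 Na-GST-1 recipients, the Na-GST-1 column equals the intercept and the rank is 4, so the effect is not estimable. The full factorial falls from 12 estimable cells to 6.

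**Step 4: if some saline recipients have natural antibody.** The protocol gives no natural anti-Na-GST-1 IgG rate; for this antigen it reports only IgE. The rate q is therefore an assumption, shown over a range:

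- expected scorable saline recipients = 30q
- P(at least one of the 6 saline cells is empty) = 1 − [1 − (1 − q)^5]^6
- P(none of the 30 scorable) = (1 − q)^30

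| Assumed q | Expected scorable of 30 | P(some saline cell empty) | P(none of 30) |
|---|---|---|---|
| 0% | 0 | 100% | 100% |
| 10% | 3 | 99.5% | 4.2% |
| 30% | 9 | 66.9% | 0.002% |
| 50% | 15 | 17.3% | under 0.001% |

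At higher q a number can be computed, but it contrasts vaccine-induced with naturally acquired antibody. Step 2 applies whatever q is.

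**Step 5: does adding SVI-10-01 rescue the factor?** Those subjects received Na-GST-1 without Na-APR-1, so they fill the lower-left cell of the Step 2 table. They add nothing at the zero level of Na-GST-1. The useful contrast is then presence or absence of Na-APR-1 among Na-GST-1 recipients, and the Na-GST-1 factor stays as uninformative as before.

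**The case against.** The best defence is the SVI-10-01 note. It is written to apply to all the analyses that follow it, which includes Objective 4. The affinity plan lists no factor levels, so a zero level of Na-APR-1 could be meant, with the model details left to the analytical plan, which is not shown. It is true that the comparator is already planned and its specimens already budgeted for assay. But the factor levels listed for IgG contain no zero for Na-APR-1, and by Step 5 the specimens do not repair the Na-GST-1 factor that plan b names.

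A second defence is that the same factor is used for IgG and for enzyme neutralisation, so nothing is peculiar to affinity. The problem of interpretation is indeed shared. Affinity differs in that missing antibody leaves no value at all.

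A third is that the trial is mainly descriptive and unpowered, with this objective tertiary. That is correct, and it limits the weight of the point.

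Two stronger readings are tempting. A reader might infer that none of the 30 saline recipients can have an anti-Na-GST-1 affinity value. The documents do not establish this: participants live in a hookworm-endemic area, and natural anti-Na-GST-1 IgG is not reported. A reader might also infer that the anti-Na-APR-1 analysis is biased because it would rest on responders only, citing section 2.1.8: "Sixty-two percent showed detectable IgG responses". That figure is natural ELISA prevalence in infected residents. It is not the share scorable by surface plasmon resonance among people assigned three doses of Na-APR-1. Selection vanishes if all respond, and gives no spurious difference if response is equal in both arms. Rules for unscorable samples commonly belong in the analytical plan, so their absence here is not a fault.

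**Conclusion.** The point holds for anti-Na-GST-1 affinity only. Within the trial, the Na-GST-1 factor in plan b, and the co-administration term in plan c, cannot show whether giving the two vaccines together lowers anti-Na-GST-1 affinity. This follows from the design alone, with no subjects given Na-GST-1 without Na-APR-1, and needs no assumption about natural antibody. Whether the effect is strictly not estimable or merely answers another question depends on how many of the 30 saline recipients have natural anti-Na-GST-1 antibody, which the protocol does not say. The three-way ANOVA stands for anti-Na-APR-1 affinity. The severity is minor: one antigen of a tertiary endpoint in a Phase 1 trial with no power claim.

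**What to change.** Reword Tertiary Objective 4, plans b and c, by antigen:

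- **Anti-Na-APR-1 affinity:** keep the three-way ANOVA and the mixed model as written.
- **Anti-Na-GST-1 affinity, within the trial:** drop Na-GST-1 as a factor and restrict both models to the 30 Na-GST-1 recipients, with Na-APR-1 dose and GLA-AF as factors (3 × 2 cells of 5).
- **Anti-Na-GST-1 affinity, effect of co-administration:** compare those 30 with the SVI-10-01 subjects from the same site who received 100 µg Na-GST-1/Alhydrogel without GLA-AF, using the specimens already to be assayed concurrently. Label the comparison non-randomised.

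The cost is wording only: no new subjects, samples or assays. The downside is reliance on a historical comparator, so differences in period or population cannot be separated from the effect of Na-APR-1. The protocol does not state how many Americaninhas subjects in SVI-10-01 received 100 µg without GLA-AF (60 there received Na-GST-1 at various doses, with or without GLA-AF), so that number should be given. In addition, 3 × 5 = 15 of the 30 co-administered subjects also receive GLA-AF with their Na-APR-1, which should be visible in the presentation.
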